8.2 Statistical Analysis

Statistical analyses will be performed by the Coordinating Center. All major treatment comparisons will be performed by intention to treat, and endpoints will be attributed to the treatment arm to which the patients were randomized, regardless of treatment crossover or post-randomization medical care. Statistical comparisons will be performed using two-sided significance tests.

8.2.1 Analysis of the Primary Endpoint

The log-rank test will be the primary analytic tool for comparing outcome differences between the two therapies. Kaplan-Meier estimates of cumulative event rates as a function of follow-up time will be calculated and displayed. Relative risks will be expressed as hazard ratios with 95% confidence intervals generated using the Cox proportional hazards model.

Supplementary analysis involving covariate adjustment will be performed with the Cox model. Such adjustment will be limited to a relatively small, prospectively defined set of patient characteristics that are known *a priori* to have a strong prognostic relationship with the primary endpoint. The covariate-adjusted analysis will serve as a prelude to supplementary analyses examining differential treatment effects. The covariates will include age, sex, race, heart failure class, presence/absence of structural heart disease, whether the patients' AF is paroxysmal, persistent or long-standing persistent, duration of AF, presence/absence of hypertension, and ejection fraction. Cox model analyses may also be performed using appropriate groupings of sites as a stratification factor.

If the data provide evidence of an overall difference in outcome between treatment groups, an assessment will be made of whether the therapeutic effect is similar for all patients, or whether it varies according to specific patient characteristics. This analysis will focus on whether the

relative therapeutic benefit differs according to patient age, sex, race, type of AF, duration of AF, heart failure class, presence/absence of structural heart disease, presence/absence of hypertension, and ejection fraction. These analyses will utilize the Cox model by testing for interactions between treatment and these specific baseline variables. In addition to the formal assessment of treatment interactions, treatment effects characterized by a hazard ratio (with 95% confidence interval) will be calculated and displayed for prospectively-defined subgroups of patients defined by the variables listed above. These descriptive hazard ratios will be carefully interpreted in conjunction with the formal interaction tests.

8.2.2 Analysis of Secondary Endpoints

Secondary endpoints, including total mortality and secondary endpoints 2 through 9 listed in Section 2.2, will all involve time-to-event analyses and thus will be analyzed similar to the primary endpoint using the log-rank test, Cox model, and Kaplan-Meier event-rate estimates.

8.2.3 Analysis of Morbidity (Adverse Events)

Statistical comparisons of major adverse events are challenging in this trial because of therapy-specific differences in the nature of the adverse events. For drug therapy, the major events include unanticipated hospitalizations for heart failure, drug-related proarrhythmic events, and pulmonary toxicity from amiodarone. For the ablation arm, the major events include myocardial perforation with tamponade requiring resuscitation, symptomatic pulmonary vein stenosis requiring intervention, and atrial-esophageal fistula formation. The frequency with which these events (and other serious adverse events) occur will be descriptively tabulated. Treatment comparisons with respect to these serious adverse events will of necessity be more informal rather than statistically rigorous (since different adverse events are expected in the two arms), bringing to bear clinical judgment as to the relative seriousness of these various adverse events. Adverse complications or adverse events of either therapy will be carefully tabulated and descriptively summarized, using statistical comparisons of the treatment groups where appropriate, and interpreting such comparisons in the context of treatment differences in the primary and major secondary clinical endpoints.

8.2.4 Analysis of Core Lab Measures of LA Size, Morphology, and Function

Patients enrolled at a subset of the clinical sites will undergo baseline and follow-up CT/MR imaging studies, and core lab measures of left atrial size, morphology, and function will be examined. Of interest will be the change in atrial size (volume) and function (i.e., atrial ejection fraction) from the baseline to the follow-up study within each treatment arm, and then importantly, a comparison of whether the change in size and function in the patients randomized to ablation therapy differs from the change in size and function of the patients randomized to drug therapy.

The distribution of these measures from the baseline and follow-up studies in each treatment arm will be descriptively characterized using univariate descriptive statistics and graphical tools such as box and whisker plots. The statistical significance of the changes in left atrial size and function from baseline to follow-up within each treatment arm will be assessed using a paired-sample test such as the paired-t test. A two-sample comparison of the two groups with respect to changes in size and function will be performed using general linear models, including the baseline value as a covariate, and assessing treatment group differences. This comparison will be performed for the changes in atrial size (left atrial volume) and also for atrial function (atrial ejection fraction).

In dealing with this type of data, the completeness of which is dependent on obtaining both the baseline and follow-up studies, there will inherently be missing data resulting from patients in

whom it is not possible to obtain both studies (because they die or fail to return for other reasons to enable the follow-up measurements to be made). Every effort will be made to minimize the amount of missing data. However, because some data are expected to be missing, several missing data strategies will be employed in order to assess the sensitivity of the conclusions to the approach used. The approaches that will be considered include (1) analyzing only patients with complete data; (2) assigning “worst case” scores to missing observations; (3) carry forward previously observed data to the observation period missed; and (4) use of likelihood-based methods to impute missing data. By synthesizing the results from these different but complementary approaches, it will be possible to provide a comprehensive assessment with respect to these key mechanistic data.

8.2.5 “On-Treatment” Analysis

Although the intention to treat analyses will serve as the standard for interpreting treatment differences in the key clinical outcomes and constitute the primary analyses in the trial, because a number of patients from the drug arm may cross over to receive ablation during the trial, we will supplement the intent to treat comparisons with “on-treatment” comparisons. The “on-treatment” analysis will involve a comparison of patients who received ablation (even if originally assigned to the drug arm) versus those who did not. Statistically, this will be accomplished using the Cox proportional hazards model with ablation included in the analysis as a time-dependent covariate. Thus, event-free follow-up time for a patient in the drug arm who later crosses over to ablation would be credited to the drug arm until the time of crossover, and at that point, the patient would be shifted to the ablation group. Because treatment assignment is no longer random, results can be biased by an association between the likelihood of treatment change and the risk of a clinical event (i.e., factors that make a patient more likely to cross over may also make them more likely to have an event). Thus such analyses should be cautiously interpreted. The “on-treatment” analyses will also include an assessment of freedom from AF in ablation patients after each ablation performed, including those undertaken after the end of the blanking period.

An analysis using a time-dependent covariate with the Cox model will also be conducted to examine the prognostic relationships of sinus rhythm with clinical outcomes. The analyses described in this section will be covariate adjusted for baseline prognostic factors that are related to the clinical outcomes of interest. These analyses will be strictly exploratory and supplementary to the primary intent to treat analyses.

8.2.6 Interim Analyses

For ethical reasons, an interim examination of key safety and endpoint data will be performed at regular intervals during the course of the trial. The primary objective of these analyses will be to evaluate the accumulating data for an unacceptably high frequency of negative clinical outcomes in any of the treatment arms. In addition, the interim monitoring will also involve a review of the control arm event rates, patient recruitment, compliance with the study protocol, status of data collection, and other factors which reflect the overall progress and integrity of the study. The results of the interim analyses and status reports will be carefully and confidentially reviewed by an NHLBI-appointed Data and Safety Monitoring Board (DSMB).

The DSMB will meet at approximately 6-month intervals to review the accumulating data. Prior to each meeting, the Statistical and Data Coordinating Center will conduct the desired statistical analyses and prepare a summary report that will be carefully reviewed by the DSMB. The extracted data files and analysis programs for each DSMB report will be archived and maintained at the Data Coordinating Center for the life of the study. Reports will be presented describing the progress of patient enrollment, the rates of compliance with therapy, and the

frequency of protocol violations. The Data Coordinating Center will also report on the number (status) of data forms completion, the number of outstanding queries, the number of queries completed, and the number of forms reviewed through on-site monitoring.

These interim safety and efficacy reports introduce well-recognized statistical problems related to the multiplicity of statistical tests performed on an accumulating set of data. To properly account for the repeated interim testing in CABANA, a group sequential method similar to that proposed by O'Brien and Fleming [105] as a guide in interpreting interim analyses will be used. This procedure requires large critical values early in the study, but relaxes (i.e., decreases) the critical value as the trial progresses. Because of the conservatism early in the trial, the critical value at the final analysis is near the "nominal" critical value. Hence the sample size requirements with this group sequential procedure remain essentially the same as the conventional fixed sample size estimate. The actual method for this interim monitoring that will be employed in CABANA is the "spending function" approach to group sequential testing developed by Lan and DeMets [106]. The Lan-DeMets approach only requires specification of the rate at which the Type I error (which in this trial will be $\alpha=0.05$ for the primary endpoint) will be "spent". This procedure allows "spending" a portion of α at each interim analysis in such a way that at the end of the study, the total Type I error does not exceed 0.05. One such spending function generates boundaries that are nearly identical to the O'Brien-Fleming boundaries. It is this approach that will be used in CABANA, namely two-sided, symmetric O'Brien-Fleming type boundaries generated using the flexible Lan-DeMets approach to group sequential testing. Since the number of looks and the increments between looks need not be predetermined, it allows flexibility in the monitoring process for accommodating additional comparative examinations of the data in response to concerns of the DSMB that may arise during the course of the trial.

The analytic approach that will be used at the interim analyses for assessing treatment differences will be the time-to-event analysis methods described previously, except that interpretation of statistical significance associated with treatment comparisons will be guided using the group sequential monitoring boundaries outlined above.

Judgment concerning the continuation or termination of the study will involve not only the degree of statistical significance observed at the interim analysis, but also the likelihood of achieving significance should enrollment continue to the originally projected sample size. As an aid in this latter assessment, the Coordinating Center will supplement the group sequential analyses outlined above with calculations of conditional power, namely the conditional probability that the treatment comparison will be significant at the end of the trial at the α level used in the design, given the hypothesized treatment difference and the data observed to date. After approximately 50% of the total events have occurred, conditional power for the primary treatment comparison will be computed and provided to the DSMB as part of the interim study reports.

8.2.7 Multiple Comparisons

With the primary hypothesis and the various secondary endpoints that have been outlined, there is a multiplicity of analyses to be performed, which leads to an increased probability that at least one of the comparisons could be "significant" by chance. Although adjustments (e.g., based on the Bonferroni inequality) could be used to preserve the overall type I error level, to adjust for the effects of the repeated significance testing that will occur as part of the interim monitoring (discussed above), plus adjust for the multiplicity of secondary endpoints, would require that very small significance levels be used for every comparison. Although the overall level of significance for the assessment of the primary composite endpoint will be 0.05, to account in

part for the multiplicity of comparisons involving secondary endpoints, a conservative approach will be taken while interpreting those results, taking into account the degree of significance, and looking for consistency across endpoints. The actual p-value for each comparison will be reported to aid in the overall interpretation.

8.2.8 Health Economics Analyses

The health economic analyses for CABANA will consist of two major parts, an empirical intention to treat cost comparison and a cost effectiveness analysis. Primary statistical comparisons between the two treatment arms of empirical costs will be performed by intention-to-treat. The patients enrolled outside the United States will be excluded from the primary cost intention-to-treat analyses. Confidence limits around the observed cost differences will be constructed using bootstrap methods.

The cost-effectiveness analyses will estimate the incremental cost required to add an extra life year with the investigational ablation arm relative to control medical therapy. In secondary analyses, we will incorporate utility weights to estimate the incremental cost per quality adjusted life year gained with ablation, relative to medical therapy. These analyses will be conducted from a societal perspective and will use a lifetime time horizon so that the estimated incremental cost-effectiveness and cost-utility ratios can be compared with societal benchmarks. We will also calculate within-trial cost-effectiveness/cost-utility ratios, although these ratios are limited in their value due to their failure to account for long-term benefits and costs and the absence of comparative benchmarks. Costs will be adjusted for inflation and both costs and life expectancy will be discounted to present value at a 3% annual discount rate. Adjustments for censored data due to staggered entry will be made following the approach of Bang and Tsiatis [107]. Extensive sensitivity analyses will be performed.

8.2.9 Quality of Life (QOL) Analyses

For each of the QOL measures examined in this study, data analysis will proceed in two stages. First, we will provide simple descriptive and comparative analyses by intention-to-treat. Second, we will examine changes over time from baseline and identify the major determinants of those changes using regression analysis. Since there is currently no consensus in the statistical literature about the best way to deal with the multiple comparisons problem arising from testing each individual scale separately, we propose two complementary approaches. First, we will pre-specify functional status (Duke Activity Status Index), AF symptom burden, and patient utilities (EuroQOL-5-D) as the primary QOL comparisons of interest and assign all other comparisons to a secondary (exploratory) status. Second, we will use the average of post-baseline values in the primary analyses of these 3 endpoints to reduce the problem of comparisons at multiple time points. Statistical power estimates for this part of our analysis show that we should have in excess of 90% power to detect $\frac{1}{4}$ SD differences in our 3 principal QOL endpoints.

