4.2 Screening and Pre-randomization Procedures

Study personnel will assess each subject against each inclusion and each exclusion criterion and the Investigator will determine the subject's eligibility for study participation. The principal investigator or documented members of the research team approved by local Institutional Review Board (IRB) or Ethics Committee (EC) will discuss the underlying rationale for the study, the procedures to be followed, the potential benefits and risks, and other issues mandated by the consent process. The informed consent process and all assessments will be documented in the subject's medical record or comparable source document. Baseline functional status, economic data (including two EQ-5D forms that rate the patient's health by using a 0-100 "thermometer" and asking 5 brief questions), and quality of life data (including a Baseline Questionnaire of validated scales, ie, SF-36, DASI, Toronto Atrial Fibrillation Severity Scale, AF Effects on QOL (AFEQT), Work Productivity and Activity Impairment Instrument (WPAI), Stanford Presenteeism scale and Mayo AF Symptom Index (MAFSI)) will be collected by the Site Coordinator via structured interview prior to randomization.

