subsequent follow-up PV and esophageal investigations. In addition at those centers, up to 150 patients randomized to drug therapy will be asked to undergo one research CT/MR scan prior to initiating therapy. This will allow the CABANA study to evaluate and compare atrial structure and function in response to drug or ablative therapy. These drug-treated patients will be recruited from selected centers that are committed to CT/MR assessment of all enrolled patients (both study arms). Since randomization is performed (stratified) within each site, this component of the study will still benefit from the overall study randomization. Optimally, the pre-therapy scans performed in all patients should be within 4 months prior to treatment.

In addition to these clinically dictated studies, baseline economic and QOL data will be obtained after informed consent is obtained, but before randomization occurs.

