4.4.2 Patient Follow Up

Follow-up in all patients will occur at 3, 6, and 12 months following randomization during the first year and every 6 months thereafter, with clinic visits, phone follow-up, and other testing as described below. Economic and QOL data, including a full follow-up questionnaire of validated scales, ie, SF-36, DASI, Toronto Atrial Fibrillation Severity Scale, AF Effects on QOL (AFEQT), Work Productivity and Activity Impairment Instrument (WPAI), Stanford Presenteeism scale, will be repeated by trained telephone interviewer staff from the EQOL Coordinating Center (EQOL CC) for patients enrolled in North America and by the Site Coordinator in sites outside North America.

Follow-up visits/calls at 3 and 6 months should be completed within 30 days +/- of the due date (Ex: 3 month visit: completed between 60 days and 120 days of randomization).

Follow-up visits/calls at 12 months and every 6 months thereafter should be completed within 60 days +/- of the due date (Ex: 12 month visit: completed between 300 days and 420 days of randomization).

Medical bills for patients enrolled at US sites will be collected throughout the trial by the EQOL Coordinating Center economic team. The Site Coordinators will complete a one page Rapid Report Form (RRF) at each CABANA study visit documenting any interim hospitalizations and/or ER visits since last contact. These forms will be forwarded to the EQOL Coordinating Center for processing. As part of the economic and QOL data in CABANA, two EQ-5D forms that rate the patient's health by using a 0-100 "thermometer", asking 5 brief questions and Mayo Atrial Fibrillation Symptom Index (MAFSI) will be collected by the Site Coordinator at 3 and 12 months following randomization during the first year and yearly thereafter throughout the trial and entered into the e-CRF.

After enrollment, subjects will either receive a single 'CABANA Box' recording system to be used throughout the entire study, or will be followed using ambulatory event and Holter ECG monitoring as generated during the course of routine clinical care as dictated by their attending physician.

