- c. The analyses described above will be extended to a multiple events analysis, designed to take into account multiple hospitalization events that may occur during the course of a patient's follow-up. When considering one event per patient as in (a) or (b) above (i.e., the time until the first event), those events are independent because they occur in different patients. When considering multiple events for a patient, the events are no longer all independent because some of them are occurring within the same patient. This correlation (covariance) must be taken into account in deriving inferences. The multiple-event methods that will be used represent different extensions of Cox model methodology, and take into account the timing of the events and the correlation among multiple events occurring within an individual patient.

The main statistical approach will use a generalization of the Cox model developed by Andersen & Gill^{6,7}, with robust standard errors to account for heterogeneity and for the correlation between recurrent events within a patient.

Similar to time-to-1st event methods, a terminal event (death) could introduce bias in the recurrent events analysis, especially if there is a differential mortality between the study arms. Thus, the Ghosh and Lin⁸ nonparametric method can be utilized in calculating the cumulative rate of CV hospitalizations, while accounting for mortality as a competing risk. In addition, the average number of CV hospitalizations per 100-person years utilizing the Ghosh-Lin method can be calculated for each treatment group.

The Andersen-Gill recurrent events method will be performed using PROC PHREG in SAS software. However, the Ghosh-Lin method requires implementation of a validated package in R software.

9.10 Medical Costs, Resource Use and Cost Effectiveness.

Cost data will be analyzed by the CABANA EQOL Coordinating Center in close collaboration with the Data Coordinating Center, and the analysis approach will be detailed in a separate analytic plan.

9.11 Quality of Life.

Quality of life data will also be analyzed by the CABANA EQOL Coordinating Center in close collaboration with the Data Coordinating Center. Again, the analysis approach will be detailed in a separate analytic plan.

9.12 Major Non-Endpoint Adverse Events.

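### Protocol 8.2.9 specifies no baseline adjustment for the primary quality-of-life comparison; adding it would narrow the intervals at no cost

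*Protocol*

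**What the plan says.** Protocol 8.2.9 is the only place in either document that describes a QOL analysis. It names functional status (DASI), AF symptom burden and EQ-5D utilities as the primary QOL comparisons and makes everything else exploratory. For these three, "we will use the average of post-baseline values in the primary analyses of these 3 endpoints"; the reason given is to limit testing at many time points.

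The section describes two stages for every QOL measure:

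- Stage one: "First, we will provide simple descriptive and comparative analyses by intention-to-treat".
- Stage two: "Second, we will examine changes over time from baseline and identify the major determinants of those changes using regression analysis".

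The baseline score is mentioned only in stage two. No test, model or covariate is named for the primary comparison.

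Baseline scores will be available. Protocol 4.2 says that the questionnaires and EQ-5D "will be collected by the Site Coordinator via structured interview prior to randomization", and Protocol 4.4.1 confirms that "baseline economic and QOL data will be obtained after informed consent is obtained, but before randomization occurs".

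For left atrial imaging, by contrast, Protocol 8.2.4 specifies a two-group linear model "including the baseline value as a covariate", and SAP 9.13 keeps that covariate. On quality of life, SAP 9.11 gives no method: "Again, the analysis approach will be detailed in a separate analytic plan". The covariate list in SAP 8.1 contains no QOL score, so it does not fill the gap.

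**The concern.** A patient's baseline score is usually a good predictor of later scores on the same instrument. When it is measured before randomization, using it as a covariate removes outcome variation that has nothing to do with treatment. A comparison of post-baseline averages that leaves it out carries that variation into the standard error.

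The stage-two regression does not do this job. It is described as a search for determinants of change, not as the primary treatment comparison.

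What is at stake is the width of the confidence intervals for the three principal QOL treatment differences. It also matters that the method is fixed in writing. With three principal endpoints in an unblinded trial, it should be clear beforehand whether the headline result is an unadjusted difference, a change score or a baseline-adjusted difference.

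**Working it through.** **Inputs**

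- Difference to detect: 0.25 SD, with power stated as above 90% (Protocol 8.2.9).
- Sample size: 2,000 to 2,200, allocated 1:1 (Protocol 8.1); 2,204 were enrolled (SAP, opening study description).
- Two-sided testing (Protocol 8.2) at a nominal 0.05 (SAP 7). No QOL-specific level is given, so 0.05/3 is also tried.
- Missing QOL data: no figure is given. The 2% loss in Protocol 8.1 concerns the clinical endpoint, so up to 40% is tried.
- Correlation r between the baseline score and the post-baseline average: not in the documents. **Assumption:** 0.4 to 0.6, with 0.3 and 0.7 shown as wider limits.

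**Step 1. Reproduce the stated power without adjustment.** Power = Φ(δ/√(2/n) − 1.96), with n per arm.

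- n = 1,000: 0.25/√(2/1000) = 0.25/0.0447 = 5.59; 5.59 − 1.96 = 3.63; power 99.99%.
- n = 600 (40% missing): 0.25/√(2/600) = 0.25/0.0577 = 4.33; 4.33 − 1.96 = 2.37; power 99.1%. At 0.05/3 it is 97.4%.
- n for 90% power: 2 × (1.960 + 1.282)²/0.25² = 337 per arm.

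The protocol's figure is a lower bound, and it is met with a wide margin without baseline adjustment.

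**Step 2. Precision gained by adjusting.** With the baseline score as a linear covariate, the variance of the treatment difference is multiplied by 1 − r² and the interval width by √(1 − r²). The unadjusted 95% half-width at 1,100 per arm is 1.96 × √(2/1100) = 0.084 SD.

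| r (assumed) | 1 − r² | Width factor | Interval narrower by | Half-width (SD) | Equivalent sample, 1/(1 − r²) |
|---|---|---|---|---|---|
| 0.3 | 0.91 | 0.954 | 5% | 0.080 | 1.10 |
| 0.4 | 0.84 | 0.917 | 8% | 0.077 | 1.19 |
| 0.5 | 0.75 | 0.866 | 13% | 0.072 | 1.33 |
| 0.6 | 0.64 | 0.800 | 20% | 0.067 | 1.56 |
| 0.7 | 0.51 | 0.714 | 29% | 0.060 | 1.96 |

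At N = 2,000 the difference detectable with 90% power falls from 0.145 SD to 0.133 SD (r = 0.4) or 0.116 SD (r = 0.6).

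**Step 3. Is 0.4 to 0.6 plausible for an average?** Averaging over visits raises the correlation with baseline. EQ-5D and the Mayo symptom index "will be collected by the Site Coordinator at 3 and 12 months following randomization during the first year and yearly thereafter", which gives six values by month 60. If every pair of visits has the same correlation c (a further assumption), then r = c/√((1 + 5c)/6). For c = 0.3 this is 0.3/√0.417 = 0.47; for c = 0.5 it is 0.5/√0.583 = 0.66. The assumed range therefore does not need a high visit-to-visit correlation. Fewer visits per patient, or correlation that fades with time, would lower r.

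**Step 4. Chance imbalance.** At 1,100 per arm the baseline difference between arms has standard error √(2/1100) = 0.043 SD, so a 95% range of ±0.084 SD. An imbalance at that limit shifts an unadjusted estimate by r × 0.084, that is 0.033 to 0.050 SD for r = 0.4 to 0.6. This is not an additional cost. It is the r² share of the variance in Step 2 seen in a single trial, and the unadjusted interval already allows for it.

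**The case against.** The strongest reply is that the quoted sentence selects a summary measure, not a model. Its stated purpose is to limit testing over visits, and an average of post-baseline values can perfectly well be the outcome in a model with baseline as a covariate. A reader might infer that the protocol has chosen an unadjusted analysis and rejected the baseline score. The documents do not support that: 8.2.9 is silent on the model, SAP 9.11 sends the method to a plan that cannot be checked here, and that plan may already adjust. Nor does the fuller imaging section show that baseline was considered and refused for QOL.

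The second reply is that nothing goes wrong without adjustment. Randomization makes the unadjusted difference unbiased on average and keeps its type I error valid, and Step 1 leaves ample power.

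Both replies stand, and they limit the point to an omission and a loss of precision. They do not remove it. Neither document specifies adjustment, and the most natural reading of the two-stage description is a simple comparison of averages first and baseline second. Deferral to another plan supplies no method. Ample power for a quarter-SD difference is no reason to report wider intervals than the collected data allow.

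**Conclusion.** The point holds as an unspecified and freely available improvement. As the text reads, the primary QOL comparison is valid but less efficient than it need be. Adjustment would narrow the intervals by 8% to 20% if the baseline score correlates 0.4 to 0.6 with the post-baseline average, and by 5% to 29% over 0.3 to 0.7. The correlation is an assumption, so the size is uncertain; the direction is not in doubt for any appreciable correlation. The stated power claim is met either way.

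Three stronger conclusions might be drawn, and none is supported:

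- **The QOL result would be biased by baseline imbalance.** It would not be, for the reason in Step 4.
- **QOL subgroup results are weakened.** Protocol 8.2.9 specifies no QOL subgroup analyses.
- **The cost-effectiveness utilities are affected.** Under Protocol 8.2.8 the main ratio is cost per life year. Utility weights enter only secondary analyses, and nothing says that they come from this comparison.

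The importance is minor, and it would disappear if the separate QOL plan already adjusts for baseline.

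**What to change.** State in Protocol 8.2.9, and carry into the separate QOL analysis plan:

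> The primary comparison of each principal QOL endpoint is the treatment difference in the average post-baseline score from a linear model adjusting for the baseline value of the same score.

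The cost is one sentence. The baseline scores are already scheduled for collection before randomization, the approach matches the protocol's own imaging analysis, and the sample size and visit schedule do not change. If the QOL plan already says this, the edit only brings the protocol into line with it.
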